1.3.2.3. Removal of Patients from the Study

Withdrawn patients are those who do not complete all evaluations and procedures outlined in the protocol because of one of the following: an AE; significant protocol deviation that, in the opinion of the PI, may compromise the study results; voluntary withdrawal; or withdrawal at the PI's discretion.

If possible, any patient who is withdrawn from the study will have, at the time of withdrawal, all exit procedures performed (see below). All clinically significant findings will be followed until resolved to the satisfaction of the PI in consultation with the Medical Monitor. If patients withdraw before or during treatment, the clinical team will seek to enroll additional patients.

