	UCN2, UCN3: Urocortins 2 and 3

PROTOCOL SYNOPSIS

Title	InTiME: Pilot Phase 1/2, Open-Label, Clinical Trial to I nvestigate CT38 in the Treatment of M yalgic E ncephalomyelitis / Chronic Fatigue Syndrome
Indication	Myalgic encephalomyelitis/chronic fatigue syndrome (ME/CFS)
Protocol Number	ME-101p
Study Sponsor	[name] Bateman Horne Center
Principal Investigator	[name] Bateman Horne Center
Study Sites	The study will be conducted at a single center in the US.
Clinical Phase	1/2
Study Period	Planned duration of the study (for each patient): 9 weeks Planned recruitment period: 12 weeks
Objectives	To evaluate the efficacy of CT38 in the treatment of ME/CFS, based on changes in patient-reported symptoms (e.g., fatigue, pain, sleep, cognition, orthostatic intolerance, temperature, flu-like, headaches or sensitivities, shortness of breath, gastrointestinal, urination, anxiety, depression), hours of upright activity, functional capacity (activity, sleep quality, energy expenditure, heart rate), and general health status (global change, vitals) To evaluate the effect of CT38 on orthostatic intolerance To gain preliminary insights on the safety and tolerability of CT38 in ME/CFS patients
Study Design	Single-center, open-label, 3-arm Phase 1/2 clinical trial The study is comprised of a screening and recruitment period, a 4-week pre-treatment assessment period, a 1-week interventional treatment period, and a 4-week post-treatment assessment period
Duration of Treatment	3.5 hours at each of Visits 3, 4 and 4b (total of 10.5 hours)
Number of Patients	Total of 18, with at least 3 in each of D1 and D2 dose groups (sequentially-dosed) and the remainder allocated to a final dose determined by D1/D2 tolerability
Study Agent	CT38s, a peptide agonist selective for the corticotropin-releasing factor receptor subtype 2, delivered by subcutaneous administration

Dosing	
The study will utilize a continuous subcutaneous infusion at 3 dose levels. The planned Low-dose delivered ~0.8 µg/kg over 3.5 hours (on 2 separate treatment days), was associated with clinically significant hemodynamic changes, and is closed out.
 
The revised doses will deliver 0.11 and 0.35 µg/kg by continuous subcutaneous infusion.

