1.2. Study Objectives

This study seeks to investigate the safety, tolerability and efficacy of CT38 in the treatment of ME/CFS patients, based on the effect of CT38 on symptom levels (e.g., fatigue, pain, sleep, cognition, orthostatic intolerance, temperature, flu-like, headaches or sensitivities, shortness of breath, gastrointestinal, urination, anxiety, depression), functional capacity (activity, sleep quality, energy expenditure, HR and

hours of upright activity), and general health status (global change, HR, BP, oral temperature, respiratory rate), pre- and post-treatment.

1.2.1. **Potential Risks**

The principal risks associated with CT38 are a potential increase in HR and decrease in BP. In the remainder of this trial, CT38 will be dosed via continuous SC infusion, repeated on 3 separate days. The original protocol lowest dose-level was associated with increased HR and decreased BP. The revised dosing utilizes lower rates of infusion and lower total doses. To mitigate risks further, dosing will be sequential, commencing with the lowest dose group and escalating only in the absence of clinically important hemodynamic changes at the preceding dose-level. HR and BP will be monitored during dosing and will have to remain within an acceptable range (see below), as a prerequisite for ascending to the next dose-level.

Beyond the investigational agent itself, there are minor risks associated with needle insertion, for blood sampling or drug administration.

1.2.2. **Potential Benefits**

If the hypothesized up-regulation of CRF₂ is correct, and if the proposed treatment achieves CRF₂ endocytosis (as it likely does in rats—based upon the loss of the ability to induce effects mediated by CRF₂ stimulation), the proposed treatment could reset the receptor within the raphe nuclei and limbic system to pre-ME/CFS levels. This should reduce the sensitivity of the stress response, thereby reducing stress-induced symptom exacerbation. If the receptor remains internalized, the treatment could be curative.

1.3. **Investigational Plan**

1.3.1. **Study Design**

1.3.1.1. *Overview*

This study is a single-center, open-label, 18-patient, 3-arm Phase 1/2 clinical trial, to evaluate safety, tolerability and efficacy of CT38, administered as the acetate salt CT38s, by the SC route of administration, at up to 3 separate dose-levels, for the treatment of ME/CFS.

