Patients who have been withdrawn from medications that interact with the 5HT, norepinephrine or dopamine signaling pathways, should have been withdrawn at least 6 weeks prior to screening and should have had 4 weeks of relative stability prior to screening in the opinion of the investigator. If patients have been recently withdrawn (at least 6 weeks) from oral corticosteroids, the investigator should be satisfied that the underlying illness for which these medications were used is stable and the risk of having to reinstate the corticosteroids over the period of the trial is low.

1.3.5. *Statistical Methods*

1.3.5.1. *Statistical Analysis Plan*

Descriptive statistics such as means, medians, standard deviations, and interquartile ranges will be generated for all continuous variables, while frequency tables will be provided for categorical and discrete variables. In addition, other exploratory statistical analyses, including stratification for disease severity and other variables, will also be performed. A significance level (p-value) of less than 0.05 will be used for all statistical tests.

1.3.5.2. *Power and Sample Size Considerations*

Given that this is a proof of concept study, no formal power calculations have been made. The study seeks to enroll up to 18 patients. Summary statistics will be performed with comparison made between pre- and post-treatment assessment periods using appropriate statistical tests.

1.3.6. *Data Quality Assurance*

The following steps will be taken to ensure the accuracy, consistency, completeness, and reliability of the data:

- Site initiation call
- Case report form review against source documents
- Data management quality control checks
- Statistical quality control checks
- Continuous data acquisition and cleaning
- Internal review of data
- Quality control check of the final report

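### A dosed patient withdrawn on the PI's judgement leaves follow-up, and no analysis set keeps that patient in the uncontrolled pre/post comparison

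*Combined protocol and SAP*

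**What the plan says.** Section 1.3.2.3 lists four grounds for withdrawal. One is an adverse event. Another is a "significant protocol deviation that, in the opinion of the PI, may compromise the study results". The last two are "voluntary withdrawal; or withdrawal at the PI's discretion". The section does not define a significant deviation, sets no time limit on discretion, and asks for no independent review of the decision; the Medical Monitor is mentioned only for following up clinical findings. A withdrawn patient has exit procedures, if feasible, when leaving. Nothing says that daily symptom scores continue. On replacement it says: "If patients withdraw before or during treatment, the clinical team will seek to enroll additional patients".

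The synopsis describes a "Single-center, open-label, 3-arm Phase 1/2 clinical trial", and section 1.3.1.1 repeats that it is open-label. The arms are dose levels given in sequence; none is a control. The primary endpoint (1.3.1.2) compares daily VAS scores for 13 symptoms before and after treatment.

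Section 1.3.5.2 states that "The study seeks to enroll up to 18 patients", with "comparison made between pre- and post-treatment assessment periods using appropriate statistical tests". Section 1.3.5.1 applies p < 0.05 to every test. Neither section names an analysis population, a rule for withdrawn or additional patients, or a missing-data method.

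**The concern.** Two of the four grounds rest on the judgement of someone who knows the treatment and can know the response. The VAS is entered online each day, including during the treatment week (1.3.3.2.5), and no section keeps the PI from the accruing scores. The team does look at outcomes as the trial runs: the amendment rationale before section 1.2 reports pre/post exercise-test findings for three D1 patients, and section 1.3.1.5.3 makes any further dosing depend on an assessment that includes efficacy.

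With no control arm, selective loss of patients cannot balance out between groups. With at most 18 patients, losing one or two who did badly moves the mean change towards benefit, and the p-value gives no sign of it. Discretionary withdrawal is usually harmless because an analysis set keeps treated patients in. This plan has no such set.

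**Working it through.** The plan gives no power, effect size, SD or dropout rate (1.3.5.2), so there is no figure to reproduce. The check has three steps.

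**1. What data a withdrawn patient leaves.** Section 1.3.1.1 gives pre-treatment Days 1-28, infusions on Days 29, 31 and 33, and post-treatment Days 36-63, which is 63 − 36 + 1 = 28 days.

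- Removed before the first infusion: there is no response to select on.
- Removed after dosing but before Day 36: there are no post-treatment scores, so no pre/post change can be formed. An additional patient is sought.
- Removed in Days 36-63: there are some post-treatment scores. Removal after Day 42, for example, leaves 42 − 36 + 1 = 7 of 28. No rule says how these are used, and the replacement sentence does not cover this period.

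**2. Illustration under no drug effect.** Let d be a patient's pre/post change in SD units, positive for improvement, with d ~ N(0,1). With m patients analysed, t = mean(d) / (s/√m). A false improvement is t above the 97.5% point of t with m − 1 degrees of freedom. The plan names neither the test nor its sidedness; I assume a paired t-test at two-sided 0.05 and count the favourable tail, so the reference is 2.5%. N = 18, with 200,000 simulated trials.

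(a) Upper bound: remove the k patients with the worst full final change; they contribute nothing, so m = 18 − k.

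(b) Treatment-week removal: early score e = ρd + √(1 − ρ²)z, with z independent N(0,1). Remove the k worst on e and add k new patients, so m = 18. The values of ρ are assumptions.

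| k removed | (a) false improvement | (a) mean shift, SD | (b) ρ = 0.3 | (b) ρ = 0.5 | (b) ρ = 0.7 | (b) mean shift, SD |
|---|---|---|---|---|---|---|
| 0 | 2.5% | 0.00 | 2.5% | 2.5% | 2.5% | 0.00 |
| 1 | 7.8% | 0.11 | 3.4% | 4.2% | 5.3% | 0.03-0.07 |
| 2 | 16.1% | 0.20 | 4.1% | 5.9% | 8.3% | 0.05-0.12 |
| 3 | 26.9% | 0.28 | 4.8% | 7.4% | 11.6% | 0.07-0.17 |

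A repeat run of (a) gave 7.7%, 15.9% and 26.7%, so the figures are good to 0.1-0.2 percentage points. The shift in (a) is the expected distance of the removed patients below the mean divided among those left: for k = 1 the unrounded 0.107 × 17 = 1.82 SD, the average position of the worst of 18.

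Early removal without replacement gives 3.4-5.4%, 4.3-9.1% and 5.1-13.3% for k = 1, 2 and 3. Replacement is therefore not what drives the bias. In a dose group of 6 (the enrolment goal in 1.3.3.2.1), losing the worst one under (a) gives 8.7% and a shift of 0.25 SD.

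**3. Removal unrelated to outcome.** If removal is independent of d, the remaining changes are still N(0,1). The shift is 0 and the rate stays at 2.5%. Keeping every treated patient in gives the same result.

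**The case against.** The wording is ordinary investigator-discretion language in a proof-of-concept study. The deviation ground needs an actual deviation first, and its natural meaning is validity, such as use of a prohibited medicine, not an unwelcome result. Discretion can serve patient welfare short of an adverse event. Section 1.3.4.6 requires departures from the regimen to be recorded, and section 1.5.1 bars the PI from deviating without written approval. All of this stands. It does not supply the missing scores or the missing analysis set.

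Four stronger readings are tempting, and the documents do not support them:

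- A reader might infer that the PI will remove poor responders. The text shows only that this is possible.
- A reader might infer that withdrawn patients are always excluded. The plan does not say so. They drop out by default if removed before Day 36; later removals leave partial scores with no stated use.
- A reader might infer that a patient can be removed on the final response and then replaced. Additional patients are sought only for withdrawals up to the end of treatment, when the Day 36-63 scores do not yet exist. Selection with replacement can use early scores at most, which is case (b).
- A reader might conclude that both grounds should be deleted. That would reach into the pre-treatment period and the PI's clinical judgement, and the bias can be removed without it.

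**Conclusion.** The concern holds as a gap in follow-up and analysis. A dosed patient can leave on the PI's judgement, the plan does not continue that patient's primary-endpoint data, and nothing keeps the patient in the comparison.

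The 7.7%, 16% and 27% are an upper bound. They need removal on the complete final change, patients who then contribute nothing, normal changes and a paired t-test. Removal on treatment-week scores with replacement gives about 3-5%, 4-8% or 5-12%, depending on the assumed correlation. The number removed is also an assumption throughout. The plan should be changed, because the cure is cheap and the damage could not be seen in the reported results.

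**What to change.** In section 1.3.2.3, keep the withdrawal grounds. Add that once a patient has received any CT38, a deviation or a PI decision may end study drug but does not end follow-up: daily VAS, upright hours and Fitbit continue to Day 63, and Visit 6 takes place, unless the patient withdraws consent. Log the reason for each removal before that patient's post-treatment scores are reviewed.

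In section 1.3.5, make the primary pre/post comparison in every patient who received any CT38, using all available post-treatment VAS. Leave patients with deviations out only in a labelled sensitivity analysis. State that additional patients add to those already treated and do not substitute for them, and report how many treated patients have no post-treatment scores.

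The cost is an amendment and analysis wording; the online VAS and the Fitbit are already in use throughout. The small downside is somewhat noisier data from patients with deviations.

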1.3.3. Study Procedures

1.3.3.1. Schedule of Events

The complete schedule of study procedures is presented in Table 6.2. While efforts will be made to comply with the schedule of events and descriptions below, the precise timing may vary, except for Visit 3, Visit 4 and Visit 4b, which each must be separated by at least 48 hours and no more than 96 hours. The pre-treatment assessment period (between Visit 1 and Visit 3) and the post-treatment assessment period (between Visit 4b and Visit 6) should each be at least 4 weeks.

1.3.3.2. Study Specific Procedures

1.3.3.2.1. Visit 1 (Day 1)

During the recruitment period up to 18 ME/CFS patients will be screened according to the inclusion/exclusion criteria with the goal of enrolling 6 patients per dose-level. Qualified patients will be invited to participate in the study.

At Visit 1, patient eligibility will be confirmed and the following will be conducted:

- Completed and signed Informed Consent Form
- Medical history, including any information on the event that triggered ME/CFS, alcohol, tobacco or nicotine-containing product use, illicit drug use, etc.
- Medication history, including prescription drug or herbal remedy within the past 3 months and non-prescription drug or vitamin within the past 2 weeks
- Physical examination, including height and weight
- Vital signs, including HR, BP (measured twice after 5 minutes sitting), oral temperature, respiratory rate
- Completed SF-36 (done prior to OI testing, see below)
- Urine pregnancy / drug screen
- Blood test (to establish eGFR, as well as standard chemistry panel and complete blood count). If the following laboratory blood tests have not been done within 3 months of the screening visit (or the results are not available) then these blood tests should be ordered as well: Lipid panel (T.Chol, HDL, LDL and TG), Total and Free Testosterone (males), ESR, CRP, Rheumatoid Factor, ANA, TSH and Free T4, Vitamin D 25-OH, Ferritin, Creatine Kinase, hemoglobin A1C, PSA (males).
- OI testing: Patients will lay supine for 5 minutes with HR and BP recorded in the last minute of supine rest. Patients will then sit upright with legs hanging over the side of the bed for 1 minute, with HR, BP and any new symptoms developing during the seated position (e.g., dizziness, visual disturbances, palpitations) recorded at the end of the 1-minute period. Patients will then stand for 10 minutes near the bed and HR, BP and any new symptoms will be recorded at 2, 5 and 10 minutes post standing. Ideally, HR should be monitored continuously with a pulse oximeter or other such device. Patients developing any symptoms suggestive of hypotension at any stage, should be rested in either the seated or supine position.

Before leaving the clinic, patients will be assigned a patient number and Fitbit Charge 2™ for continuous monitoring (activity, sleep and HR) throughout the trial..

1.3.3.2.2. Pre-Treatment Assessment Period (Days 1-28)

In the 4-week pre-treatment assessment period, patients will utilize the wearable Fitbit Charge 2™ to record activity, sleep-related data and HR, and complete the daily VAS (online), and daily hours of upright activity (online). Patients will also record any changes in medication use, any AEs and other qualitative observations (online).

1.3.3.2.3. Visit 3 (Day 29)

At Visit 3 (Day 29) patients will complete SF-36 and undergo a brief physical exam, recording vitals and any patient-recorded changes in medications, AEs and other qualitative observations during the pre-treatment recovery period. A urine pregnancy test will be performed prior to study drug administration. In addition, patients will have an intravenous catheter placed in the arm to facilitate blood sampling for PK assessment. Following this, the study drug will be administered as outlined above, beginning at approximately 10am.

Patients should be semi-recumbent before and during the infusion procedure. Prior to the infusion, duplicate measures of HR and BP should be made after 10 minutes in the semi-recumbent position. The duplicate measures should be averaged and the average of the HR, systolic and diastolic BP will represent baseline (Time Zero). These baseline values should be recorded and the infusion stopping criteria (Section 6.3.1.6) should be annotated prior to the start of the infusion for reference purposes. During the procedure, HR and BP will be monitored every 15 minutes throughout the infusion period and for a minimum of 90 minutes post infusion. The post infusion vital sign monitoring may be prolonged as appropriate until clinically stable. PK samples will be obtained prior to the onset of study drug administration, and at 45 minutes, 90 minutes, 210 minutes (after stopping infusion) and at 300 minutes (before the patient is allowed to go home). All AEs will be assessed and recorded as well as the need for any medications. Provided patients are clinically stable they may leave the clinic at 2 hours post-infusion.

1.3.3.2.4. Visit 4 (Day 31)

At Visit 4 (Day 31) patients will undergo a brief physical exam, recording vitals and any patient-recorded changes in medications or AEs. Following this, the study drug will be administered as outlined above (see Visit 3), beginning at approximately 10am.

Both before and during the infusion procedure, HR and BP will be monitored exactly as described for Visit 3, and blood samples for PK assessment will be obtained, per the schedule at Visit 3. All AEs will be assessed and recorded as well as the need for any medications.

1.3.3.2.5. Visit 4b (Day 33)

At Visit 4b (Day 33) patients will undergo a brief physical exam, recording vitals and any patient-recorded changes in medications or AEs. Following this, the study drug will be administered as outlined above (see Visit 2), beginning at approximately 10am.

Both before and during the infusion procedure, HR and BP will be monitored exactly as described for Visit 3, and blood samples for PK assessment will be obtained, per the schedule at Visit 3. All AEs will be assessed and recorded as well as the need for any medications. Treatment Period (Days 29-36)

Throughout the 1-week treatment period (including treatment days), patients will utilize the wearable Fitbit Charge 2™ to record activity, sleep-related data and HR, and complete the daily VAS (online), and daily hours of upright activity (online). Patients will also record any changes in medication use, any AEs and other qualitative observations (online).

1.3.3.2.6. Post-Treatment Assessment Period (Days 36-63)

Throughout the 4-week post-treatment recovery period, patients will utilize the wearable Fitbit Charge 2™ to record activity, HR and sleep-related data, and complete the daily VAS (online), and daily hours of upright activity (online). Patients will also record any changes in medication use, any AEs and other qualitative observations (online).

1.3.3.2.7. Visit 6 (Day 64)

At Visit 6 (Day 64), patients will undergo a final checkup, including physical examination, recording vitals and any updates to patient history. Patient will be required to complete SF-36, followed by OI testing conducted exactly as at Visit 1. All AEs will be assessed and recorded as well as the need for any medications.

1.3.3.3. Safety Assessments

Specific safety parameters and procedures will be as follows:

- Clinical observation and assessment of AEs
- Subjective symptoms and complaints via individual interviews
- Vital signs, including HR, BP, oral temperature and respiratory rate. Abnormal BP readings will be treated and followed as appropriate
- Physical examination as required

When an AE is suspected, all relevant evaluations will be carried out and appropriate treatment provided. Additional follow-up will be performed as necessary, recorded in the patient's source documents, with the results provided to the PI. Patients who experience any clinically significant AE will remain under medical supervision until the PI, in consultation with the Medical Monitor, deems the AE to be resolved, stabilized, or no longer serious enough to warrant follow-up.

Note that prior to dose, only serious, procedure-related AEs will be captured on the AE case report form). For AE definitions and reporting requirements, see below.

1.3.4. Study Agent

1.3.4.1. Formulation, Appearance, Packaging, and Labeling

All study medication will be supplied by Cortene in sterile single-use vials.

CT38 Concentrate will be supplied in Schott 6R vials containing 1 ml of 1 mg/ml concentration... [proprietary data redacted].

Diluent for CT38 Concentrate will be supplied in Schott 6R vials containing 6 ml of... [proprietary data redacted].

